Annex 4 NaTHNaC/PHS yellow fever pre-vaccination checklist (Traveller's checklist)¹²

Checklist: yellow fever vaccine

This pre-vaccination checklist assists your healthcare professional to assess the risk of giving you yellow fever vaccine, **they must review the checklist** to ensure the vaccine is safe for you.

If you have any questions, concerns or do not understand anything please ask your healthcare professional to explain during your consultation.

If you answer 'yes' to any questions, you need to give more details during your consultation.

To read more about why these questions are important, please see page 3 and page 4 of this form.

Q1	How old are you?		
Q2	Are you feeling unwell today?	Yes	No
Q3	Do you have any allergies, particularly to eggs or chicken protein?	Yes	No
Q4	Have you ever reacted to a previous yellow fever vaccine?	Yes	No
Q5	Do you have cancer or have you had cancer in the past (even if it was a long time ago)?	Yes	No
Q6	Do you have any illness that might affect your immune system? For example, leukaemias, lymphoma, cellular immune deficiencies, chronic lymphoproliferative conditions, or if you have ever received a stem cell transp	Yes	No 🗌
Q7	Are you living with HIV?	Yes	No
Q8	Are you taking any medicines (now or within the last year) that affect your immune system? For example, steroids, biological or non-biological immune modulating medicines, treatment following an organ transplant.	Yes	No
Ga Ga	Are you having chemotherapy or radiotherapy (now or within the last year)?	Yes	No

Have you ever been told that your thymus gland (includes r	myasthenia gravis or a thymoma)?	Yes	No
Have you had an operation to			
Have you had an operation to (thymectomy) for any reason	remove your thymus gland including during cardiac surgery?	Yes	No
(,			1000
Have you ever had open chest	surgery?	Yes	N
Are you pregnant or planning	a pregnancy?	Yes	No
Are you breast feeding?		Yes	N
		\$1 - Ab	
	nily relative (i.e. a blood relative –		
adverse reaction to yellow fev	ster or child) who has had a serious	Yes	N
	nfirm that the questions have been a	nswered to the	e
best of my knowledge.	•		
	ofirm that the questions have been a Signature of patient	Date (dd/m	
best of my knowledge.	•		
best of my knowledge. Name of patient	•		
Name of patient If applicable	Signature of patient	Date (dd/m	ım/
best of my knowledge. Name of patient If applicable	•		ım/
best of my knowledge. Name of patient If applicable	Signature of patient	Date (dd/m	ım/
best of my knowledge.	Signature of patient	Date (dd/m	ım/
best of my knowledge. Name of patient If applicable	Signature of patient Signature of parent/guardian	Date (dd/m	ım/
Name of patient If applicable Name of parent/guardian	Signature of patient Signature of parent/guardian	Date (dd/m	ım/

Why are these questions important?

How old you are

Babies

There is a greater risk of yellow fever vaccine related brain inflammation (encephalitis)
in very young babies. Babies aged less than six months should not have yellow fever
vaccine and babies aged six to nine months should only be given this vaccine if the
risk of yellow fever at the destination to be visited is high, such as during epidemics/
outbreaks, and travel is unavoidable.

Aged 60 years or older

You are at increased risk of developing serious side effects from the vaccine compared to
younger travellers. If you are travelling to areas where yellow fever vaccine is 'generally
not recommended' you should not receive vaccine. Further information is available in
the NaTHNaC Yellow Fever Information Leaflet for Travellers and on the FitForTravel
Yellow Fever Vaccine page.

How you are feeling today

 Minor illness without high temperature (fever) should not usually delay your yellow fever vaccination. However, vaccination may be postponed until you have fully recovered.
 This is to make sure any symptoms are not confused with possible reactions to the vaccine.

Your allergies and previous reactions to yellow fever vaccine

This vaccine may contain traces of egg, chicken protein and other ingredients that some
people are occasionally allergic to. If you have ever had a serious reaction (anaphylaxis)
to any of the vaccine ingredients, you must tell your health professional; you will not
usually be able to receive yellow fever vaccine.

Your general health and any condition or treatment that may affect your immune system

This vaccine contains live yellow fever virus that has been weakened. Your response to
the vaccine may not be so good if your immune system is weakened by certain illnesses
or treatments, but occasionally the vaccine can still be given. However, if your immune
system is very weak you must not receive yellow fever vaccine as you are at risk of
developing serious side effects from the vaccine, including death.

31-May-2023

Version number: 3.0

If you have ever been told that you may have a problem with your thymus gland (includes myasthenia gravis or a thymoma), or if you ever had open chest surgery

- The thymus gland is part of your immune system and sometimes does not work properly
 or has been removed (thymectomy). Myasthenia gravis is a disease that may involve
 your thymus gland. If you have a history of any of these conditions, you must not receive
 yellow fever vaccine as you are at risk of developing serious side effects, including death.
- The thymus gland may be removed during chest surgery. Yellow fever vaccine can still be given in some instances following chest surgery.

If you are planning a pregnancy, pregnant now or breast-feeding

- If you are planning a pregnancy, it is recommended to wait until 28 days after yellow fever vaccination before getting pregnant (conceiving).
- Safety of yellow fever vaccine during pregnancy is not clear, although increased
 complications for mother or baby have not been reported when the vaccine was given
 during pregnancy. Discussion with a health professional about the risks and benefits of
 this vaccine during pregnancy will help you decide whether yellow fever vaccination is
 right for you at this time.
- You are encouraged to continue breast-feeding during your trip. Several very young (less than two months old) breast-fed babies developed brain inflammation shortly after their mothers' yellow fever vaccination. Discuss with a health professional whether the risk of yellow fever at your travel destination is sufficiently high for yellow fever vaccination to be recommended.

If you have a first-degree family member who has had a serious adverse reaction to yellow fever vaccine

 If such a reaction was not due to a known medical risk factor, it is possible that you may be susceptible to developing a serious adverse reaction due to an unidentified genetic reason.

If you cannot have the yellow fever vaccination, and travel to areas where yellow fever occurs cannot be avoided, you still need advice about yellow fever certificate requirements and how to avoid mosquito bites.

Please check the following websites for further information and updates:

- TravelHealthPro www.travelhealthpro.org.uk/countries
- Fit for Travel www.fitfortravel.nhs.uk/yellow-fever-vaccine

For healthcare professionals:

- TravelHealthPro www.travelhealthpro.org.uk
- TRAVAX (Scotland) www.travax.nhs.uk/yellow-fever

Annex 5 AE Form

Unsolicited Individual Safety Information (ISI) Report Form

Grey fields are for Sanofi use only

1 ADMINISTRATIVE SECTION FOR AFFILIATE/PARTNER ONLY						
Company contact date: Click or tap to enter a da	te. Local PV receipt date: Click or tap to enter a date.					
Country of Occurrence: Click here to enter text.						
Social Media case: Yes □ No □ If Yes: Nan	Social Media case: Yes ☐ No ☐ If Yes: Name of the social media: Click here to enter text.					
□INITIAL □ FOLLOW-UP Global Safety Da	□INITIAL □ FOLLOW-UP Global Safety Database ID: Click here to enter text.					
Local Reference ID: Click here to enter text. Local	I PTC ID: Click here to enter text. Global PTC ID: Click here to enter text.					
2 PATIENT						
Title, Name (first, middle, last)/Initials: Click he	Title, Name (first, middle, last)/Initials: Click here to enter text. Gender: F □ M □ Unk □					
Address, city, postal code, state: Click here to enter text.						
Country: Click here to enter text. Phone: Click here to enter text.						
Email address: Click here to enter text.						

2	$P \Delta$	TI	F	N	т

3 REPORTER

Date of Birth (DD/MM/YYYY): Click or tap to enter a date. Age or Age Group (at time of the reaction): Click here to enter text.

Height: Click here to enter text. cm/feet & inches Weight: Click here to enter text. kg/lb Registry ID #: Click here to enter text.

First Name: Click here to enter text. Last Name: Click here to enter text.
Occupation: Click here to enter text.
Address: Click here to enter text.
Zip / Postal Code: Click here to enter text.
Country: Click here to enter text.
Phone: Click here to enter text.
Fax: Click here to enter text.
E-mail address: Click here to enter text.
If the primary reporter is a consumer, is contact information provided for a HealthCare Professional? *Yes □ No □ NA □

Property of the Sanofi Group - strictly confidential

Was FU request sent to reporter? Yes \square No \square NA \square

Page 71

If your country requires patient consent to contact the HCP, has the patient given their consent? *Yes \subseteq **No \subseteq NA \subseteq

*If YES, attempts should be made to contact the HCP **If NO, do not contact the HCP and document the exchange

31-May-2023	
Version number:	3.0

3 REPORTER
The reporter will not have any further information □
The reporter does not wish to be contacted by the Pharmacovigilance Department \square

4 SUSPECT MEDICATION / MEDICAL DEVICE (MD) / VACCINE (V)

Brand Name /INN	Indication	Dosage/ Unit/ Frequency/ Amount	Batch Number (Mandatory. If not available, enter NA/ if not obtainable at all enter NO)	Start Date (DD/MM/YYYY)	Stop Date or duration (DD/MM/YYYY)	Route of Administration	Company product (Yes/No)	Primary/Booster (V)	Site of Injection (V)	Side (V)
Click here to enter text.										
Click here to enter text.										
Click here to enter text.										
Click here to enter text.										
Click here to enter text.										
Click here to enter text.										

31-May-2023	
Version number:	3.0

Is medical device available for evaluation (MD)? □Yes □No
Did the problem occur with initial use or during re-use of the medical device (MD)? \square Yes \square No
For company suspect product inappropriately used as per local Marketing Authorization:
Is it intentional? □Yes □No □Unk at the initiative of □HCP □Consumer □Unk for a therapeutic purpose? □Yes □No □Unk
Comments (Complementary information: presentation, syringe, single dose, multidose, storage conditions): Click here to enter text.

5 CONCOMITANT MEDICATION / MEDICAL DEVICE / VACCINE

Brand Name /INN	Indication	Dosage/ Unit/ Frequency/ Amount	Batch Number	Stop Date or duration (DD/MM/YYYY)	Route of Administration	Company product (Yes/No)	Primary/ Booster (V)	Site of Injection (V)	Side (V)
Click here to enter text.									
Click here to enter text.									
Click here to enter text.									
Click here to enter text.									
Click here to enter text.	_								
Click here to enter text.									

31-May-2023	
Version number: 3.0	

Click here to enter text.					
Click here to enter text.					

6 REACTION DESCRIPTION									
Reaction	Date of Onset (DD/MM/YYYY)	Stop Date or Duration (DD/MM/YYYY)	Outcome	Corrective Treatment	Action Taken	Did reaction abate after product was stopped?	Did reaction recur after product was started again?	Kind of Reaction (V)	Lack of efficacy / failure (V)
Click here to enter text.									
Click here to enter text.									
Click here to enter text.									
Click here to enter text.									
Click here to enter text.									

7 DESCRIPTION OF THE CASE (signs & symptoms, possible causes, progression, treatments, relevant medical history, investigations, severity)
Click here to enter text

8 ONGOING ILLNESS / MEDICAL HISTORY / RISK FACTORS

Personal (if relevant for the reaction described in this form): Click here to enter text.

Family (if relevant for the reaction described in this form): Click here to enter text.

9 HISTORY OF ADVERSE REACTION TO PREVIOUS ADMINISTRATION OF VACCINE (V)

Product Name / Therapeutic Class	Date of Occurrence	Reaction	Duration
Click here to enter text.			
Click here to enter text.			
Click here to enter text.			

Comments: Click here to enter text.

10 COMPLEMENTARY INVESTIGATIONS Type / Results (indicate unit / attach photocopies if relevant. If patient died please specify if autopsy was performed and what was result)

Click here to enter text.

31-May-2023

Version number: 3.0

Annex 6 Assessment of success

6.1 Assessment of success (HCP questionnaire)

Objectives	Questions	Is the question included in the assessment of success? (Yes/No)	Definition of desirably/correctly answered question	Assessment of success
	Q1. According to your knowledge about the conditions of use for STAMARIL® (yellow fever vaccine), which of the following statements do you agree/disagree with? Please select all options that apply	Yes	Question completed correctly [5 points (3 True and 2 False)]	
Knowledge and Understanding (5 questions)	Q2. According to your knowledge about the risks associated with STAMARIL® (yellow fever vaccine) administration, which of the following statements do you agree/disagree with? Please select all options that apply	Yes	Question completed correctly [4 points (2 True and 2 False)]	An HCP is considered successful for knowledge and understanding when he/she provides at least 22 out of 27 (80%) correct/desirable
(5 questions)	Q3. According to your knowledge about STAMARIL® (yellow fever vaccine), this vaccine is contraindicated in the following circumstances: Please select all options that apply	Yes	Question completed correctly [10 points (7 True and 3 False)]	responses. Success for knowledge if ≥80% of HCPs are successful.
	Q4. According to your knowledge about the risks associated with STAMARIL® (yellow fever vaccine) administration, which of the following are the possible side effects of this vaccine? Please select all options that apply.	Yes	Question completed correctly [5 points (4 True and 1 False)]	

Objectives	Questions	Is the question included in the assessment of success? (Yes/No)	Definition of desirably/correctly answered question	Assessment of success	
	Q5. According to your knowledge about STAMARIL® (yellow fever vaccine) administration to pregnant/breastfeeding women, which of the following statements do you agree/disagree with? Please select all options that apply	Yes	Question completed correctly [3 points (2 True and 1 False)]		
Awareness (2	Q6. Please select the option that best describes your experience with the standardised yellow fever pre-vaccination checklist(s).	Yes	Question completed desirably [Answers: 1 or 2 are desirable]	An HCP is considered successful for awareness when he/she is aware of the UK (STAMARIL®) yellow	
questions)	Q7. Please select which of the following standardised yellow fever pre-vaccination checklist(s) you have received or are aware about: Please select all options that apply	Yes	Question completed desirably [Answer: 1 is desirable]	fever pre-vaccination checklist Success for awareness if ≥80% of HCPs are successful.	
	Q8. Please select the option that best describes your experience with the use of the yellow fever pre-vaccination (STAMARIL®) checklist issued by the Medicines and Healthcare products Regulatory Agency (MHRA)	Yes	Question completed desirably [Answers: 1 or 2 are desirable]	An HCP is considered successful for utilization when he/she utilizes either the UK (STAMARIL®) yellow fever pre-vaccination	
Utilization (7 questions)	Q9. Please select the option(s) that best describes why you never/rarely/sometimes use the yellow fever pre-vaccination (STAMARIL®) checklist issued by the Medicines and Healthcare products Regulatory Agency (MHRA): Please select all options that apply	No	Complementary question	yellow fever pre-vaccination checklist or traveller checklist Success for utilization if ≥80% of HCPs are successful.	

Page 78

Objectives	Questions	Is the question included in the assessment of success? (Yes/No)	Definition of desirably/correctly answered question	Assessment of success
	Q10. Please select the option(s) that best describes the challenges you face while using the yellow fever pre-vaccination (STAMARIL®) checklist issued by the Medicines and Healthcare products Regulatory Agency (MHRA): Please select all options that apply	No	Complementary question	
	Q11.Please select the option that best describes your experience with the use of the yellow fever pre-vaccination checklist (i.e. traveller checklist) issued by the National Travel Health Network and Centre (NaTHNaC) and Public Health Scotland (PHS)	No	Question completed desirably [Answers: 1 or 2 are desirable]	
	Q12. Please select the option(s) that best describes why you never/rarely/sometimes use the yellow fever pre-vaccination checklist (i.e., traveller checklist) issued by the National Travel Health Network and Centre (NaTHNaC) and Public Health Scotland (PHS): Please select all options that apply	No	Complementary question	
	Q13. Please select the option(s) that best describes the challenges you face while using the yellow fever pre-vaccination checklist (i.e., traveller checklist) issued by the National Travel Health Network and Centre (NaTHNaC) and Public Health	No	Complementary question	

Objectives	Questions	Is the question included in the assessment of success? (Yes/No)	Definition of desirably/correctly answered question	Assessment of success
	Scotland (PHS): Please select all options that apply			
	Q14. Please provide any additional comment you may have on the checklist(s).	No	Complementary question	
Distribution of the	Q15.Please select the option that best describes your experience with the delivery of the STAMARIL® (yellow fever vaccine) Patient Information Leaflet (PIL)	Yes	Question completed desirably [Answers: 1 or 2 are desirable]	An HCP is considered successful for delivery of the STAMARIL®
STAMARIL® PIL (2 questions)	Q16. Please select the option(s) that best describes why you never/rarely/sometimes deliver the STAMARIL® (yellow fever vaccine) Patient Information Leaflet (PIL): Please select all options that apply	No	Complementary question	PIL when he/she always/frequently distributes the STAMARIL® PIL

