UK (STAMARIL®) yellow fever pre-vaccination checklist (for HCPs) (Annex 3)

Following two fatal adverse reactions to yellow fever vaccine in the UK in 2018-2019, due to unapproved use in both cases, the UK MHRA requested the MAH to add a standardised UK checklist, developed by MHRA (hereby referred to as 'UK (STAMARIL®) yellow fever prevaccination checklist' in this protocol), as part of local additional risk minimisation measures (aRMMs) in the STAMARIL® Risk Management Plan, to support the UK healthcare professionals (HCPs) in the benefit-risk assessment process. The objective of this checklist is to ensure compliance of HCPs from designated authorised YFVCs with indications, contraindications, warnings, and precautions of the yellow fever vaccine as per the Summary of Product Characteristics (SmPC) and to support the appropriate evaluation of individual travellers' risk-benefit balance. The most recent SmPC (dated 15 Feb 2021) details the required considerations of risk-benefit balance for individual travellers. The UK (STAMARIL®) yellow fever pre-vaccination checklist (Annex 3 has been published on 16 Nov 2021, on the MHRA Drug Safety Update website. ¹⁰

NaTHNaC/PHS yellow fever pre-vaccination checklist (Traveller's checklist) (Annex 4)

In the UK, NaTHNaC first published a yellow fever pre-vaccination checklist in July 2019, which was updated in January 2020 in accordance with the recommendations in the Commission on Human Medicine's Expert Working Group report. In September 2021, NaTHNaC and PHS produced a new version of the yellow fever pre-vaccination checklist (Annex 4). This checklist is a screening tool and is intended for vaccinees (travellers) to read and complete in advance of, or during, the travel health consultation; it is also commonly called the 'traveller's checklist'. Based on the Annual Return 2020 report published by NaTHNaC, >90% of YFVCs in England, Wales, and Northern Ireland used a traveller (vaccinee) checklist during the travel health consultation to assist with yellow fever vaccine risk assessment. The contents of this checklist are similar to that of the UK (STAMARIL®) yellow fever pre-vaccination checklist. Therefore, throughout this protocol, 'standardised yellow fever pre-vaccination checklist' refers to either or both these checklists (i.e. 'UK (STAMARIL®) yellow fever pre-vaccination checklist' and 'NaTHNaC/PHS yellow fever pre-vaccination checklist').

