The questions considered as complementary will not be included in the assessment of success. The details of the assessment of the success for each survey and each objective is described in Annex 6.

Success at the HCP/vaccinee level will be defined for each primary objective based on the number of sub-questions related to that objective being completed with desirable responses. A HCP/vaccinee will be successful in each objective (except knowledge and understanding for HCPs) if all related questions, including sub-questions, will be completed with desirable responses (Annex 6). An HCP will be successful for knowledge and understanding of any standardised yellow fever pre-vaccination checklist(s), if at least 80% of the related questions, including sub-questions, are completed with desirable responses.

A threshold of 80% successful HCPs or vaccinees on each of the primary outcomes would be considered appropriate for assessing the effectiveness of an aRMM.

It should be noted that the selection of this threshold for success is subjective and not based on *a priori* knowledge, experience, or established scientific criteria in the education or risk communication or evaluation literature. If additional information from published literature becomes available at the time of reporting, then the results will be discussed in the context of this new information. The methods of reporting and analysis of results obtained will be done as already described in this protocol and will be further detailed in the statistical analysis plan (SAP).

Description of characteristics of HCPs with desirable/undesirable responses

The charactertistics of HCPs with desirable and undesirable responses to questions related to each outcome will be described using all available and relevant participant information collected in the survey (i.e. region, HCP profession, gender, age range, duration of practice, type of setting, years of professional experience and experience with STAMARIL®). This will be further detailed in the SAP.

Description of characteristics of vaccinees with desirable/undesirable responses

The characteristics of vaccinees with desirable and undesirable responses to questions related to each outcome will be described using all available and relevant participant information collected

in the survey (i.e., age range, region, gender, and education level). This will be further detailed in the SAP.

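### The pooled 22-of-27 knowledge rule has no minimum for the contraindication question, and the planned per-question result would not show a weakness there

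*Protocol*

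**What the plan says.** Annex 6.1 of the Protocol scores five knowledge questions by item. Q1, on conditions of use, has "Question completed correctly [5 points (3 True and 2 False" items; Q2, on risks, "Question completed correctly [4 points (2 True and 2 False"; Q4, on side effects, "Question completed correctly [5 points (4 True and 1 False"; and Q5, on pregnancy and breastfeeding, has 3 points. Q3 asks whether "this vaccine is contraindicated in the following circumstances" and carries the most: "Question completed correctly [10 points (7 True and 3 False" items. An HCP succeeds "when he/she provides at least 22 out of 27 (80%) correct/desirable" responses, and knowledge succeeds if at least 80% of HCPs do.

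Section 9.7.1 states the same pooled rule: an HCP succeeds "if at least 80% of the related questions, including sub-questions, are completed with desirable responses". Table 1 agrees. None of these places sets a minimum for a single question.

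Two other outputs touch on single questions. Table 1 and section 9.7.1 plan the proportion of HCPs with a desirable response to each question, but section 9.7.1 lets one right answer suffice where a question takes several answers or is true/false. Section 9.7 reports how often each option was chosen and sets combinations of answers aside.

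**The concern.** The rule is compensatory: right answers on side effects or conditions of use offset contraindications that were not recognised. Section 7 gives the checklist's purpose as compliance with indications, contraindications, warnings and precautions, and says it was requested after two fatal reactions "due to unapproved use in both cases". The contraindication part of the checklist (Annex 3) is not compensatory, since a single yes rules vaccination out.

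The composite is the only knowledge success indicator. If it can be met while most HCPs miss three or more of the ten contraindication items, an unqualified statement that the key safety messages are known would mislead on one of the main messages.

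**Working it through.** **Inputs (Annex 6.1).** Items: Q1 = 5, Q2 = 4, Q3 = 10, Q4 = 5, Q5 = 3. HCP pass mark: 22. Survey threshold: 80% of HCPs.

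**The plan's own figure.** 5 + 4 + 10 + 5 + 3 = 27. 0.80 × 27 = 21.6, so the smallest whole pass mark is 22 (22/27 = 81.5%; 21/27 = 77.8%). The mark reproduces, and its 80% label is a harmless rounding.

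**What the rule allows.** Errors allowed: 27 − 22 = 5. Lowest passing Q3 score: 22 − 17 = 5 of 10. The five errors may all fall among the seven true contraindications, leaving 2 of 7 recognised. Q3 wholly wrong gives at most 17 of 27, a fail. The smaller questions can be wholly wrong: Q1 leaves 22, Q2 23, Q4 22 and Q5 24, all passes.

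**Survey level.** Assume independent items and equally knowledgeable HCPs, with accuracy p on each Q3 item and q on each of the other 17. Then

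P(pass) = sum over i + j ≥ 22 of Bin(i; 17, q) × Bin(j; 10, p).

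With q = 1 this reduces to P(Bin(10, p) ≥ 5).

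| Q3 accuracy p | Pass, q = 1.00 | Pass, q = 0.95 | Pass, q = 0.90 | At least 8 of 10 on Q3 |
|---|---|---|---|---|
| 0.50 | 62.3% | 43.1% | 28.0% | 5.5% |
| 0.60 | 83.4% | 65.3% | 47.4% | 16.7% |
| 0.70 | 95.3% | 83.6% | 67.8% | 38.3% |
| 0.80 | 99.4% | 94.7% | 84.7% | 67.8% |

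- With everything else right, the expected pass share crosses 80% between p = 0.58 (79.8%) and p = 0.60 (83.4%). At p = 0.60, 17% of HCPs have 8 of 10 on Q3.
- At q = 0.95 and p = 0.70 the indicator is expected to be met (83.6%). 38.1% of HCPs both pass and reach 8 of 10, so (83.6 − 38.1)/83.6 = 54% of those who pass are below 8 of 10. All ten right: 0.7^10 = 2.8%.
- At q = 0.90 and p = 0.70, 68% pass and the indicator is not met.
- Under guessing (p = 0.50) at most 62.3% pass. With the minimum sample of 200 HCPs, the chance of observing at least 160 passes is then about 5 in 100 million.

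**Would the per-question result show it?** If one right answer makes Q3 desirable, an HCP who guesses every item counts as desirable with probability 1 − 0.5^10 = 99.9%. The result would sit near 100% whatever the true knowledge. The option frequencies of section 9.7 would show accuracy item by item, but not how many HCPs know most of the contraindications.

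**The case against.** A reader might infer that knowledge could be declared successful while contraindication knowledge is absent or no better than guessing. The table contradicts this: guessing on Q3 fails the 80% indicator clearly, and an HCP with Q3 wholly wrong fails individually. A reader might also infer that Q3 measures the very knowledge that would have prevented the two deaths. Section 7 does not say what the unapproved use was, and the checklist's purpose also covers indications, warnings and precautions. The item texts are in a stand-alone questionnaire that is not shown, so the other questions may bear on unapproved use too.

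Other points have weight. The troubling scenarios need Q3 to be clearly weaker than the rest, and nothing in the Protocol predicts that among HCPs trained within the past 24 months. Q3 already has the largest weight, 10/27 = 37%. The Protocol calls its 80% threshold subjective. Having all ten right is not a Protocol standard, and even 90% accuracy per item gives only 0.9^10 = 35%. Making Q3 a veto on a primary success claim after data collection began in March 2023 would be a debatable trade-off.

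The best defence is that per-question proportions are already planned with confidence intervals. It would answer the point if those proportions were informative, but the one-right-answer criterion makes them nearly uninformative for a ten-item question. The admission about the threshold concerns its level, not pooling across messages.

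**Conclusion.** The point stands as a weakness in how the knowledge result will be read, not as an error in the pass mark. An HCP can succeed with 5 of 10 contraindication items right. The survey indicator can be met with Q3 accuracy of about 60% (all else right) to 70% (95% right elsewhere), when only 17% to 38% of HCPs have 8 of 10 right. The planned per-question result would not show this.

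The HCP-level statement is exact. The survey-level figures assume independent items and equal accuracy across HCPs, and they depend on high accuracy elsewhere: at 90%, Q3 accuracy of 70% no longer meets the indicator. The documents support a clearer report, not a claim that the indicator passes without contraindication knowledge.

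**What to change.** 1. Keep the 22-of-27 composite, with 80% of HCPs, as the success indicator.
2. In section 9.7.1 and Annex 6.1, drop the one-right-answer criterion for Q1 to Q5 and use the item scoring of Annex 6.1 for the per-question results.
3. Report beside the composite the proportion of HCPs with at least 8 of 10 Q3 items right, which is the Protocol's own 80% applied to that question, with its 95% Wilson interval. Give the proportion with all ten right as description only, without a threshold.
4. State in advance that, if the composite is met but the Q3 proportion is below 80%, the report will say so and name contraindications as a message not adequately known, rather than state knowledge success without qualification.

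This needs one extra derived variable from answers already collected, and no new question or respondent. The downside is a possibly less favourable knowledge statement. The Q3 benchmark is demanding: under the same assumptions, 80% of HCPs reach 8 of 10 only at about 84% accuracy per item. That is a reason to report it beside the indicator and not to make it a veto.
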